4.2.1.2 Management of liver enzyme elevation

The guidelines for managing liver enzyme elevations are the same as is in the parent protocols. The following procedures are based on the *FDA Guidance for Industry. Drug-Induced Liver Injury: Premarketing Clinical Evaluation (P09-12413)*.

ALT or AST > 1.5 fold ULN and < 3 fold ULN

- Continue as planned

ALT or AST \geq 3 fold ULN and < 5 fold ULN with no signs of severe liver damage

- Reduce to 100 mg bid or interrupt treatment (to be decided by investigator, based on individual risk assessment)
- Re-test ALT and AST, as well as alkaline phosphatase, total bilirubin and eosinophils within 48 to 72 hours, then at approximately 7 days, then at approximately 2 weeks, and assess signs of severe liver damage:
 - If ALT and AST < 3 fold ULN after 2 weeks, return to initial dose if reduced, restart at reduced dose if interrupted. Monitor lab (see above) every 2 weeks for at least 8 weeks.
 - If ALT and/or AST \geq 3 fold ULN after 2 weeks or any time thereafter, permanently discontinue study medication.

ALT or AST \geq 5 fold ULN and < 8 fold ULN with no signs of severe liver damage

- Interrupt treatment.
- Re-test ALT and AST, as well as alkaline phosphatase, total bilirubin and eosinophils within 48 to 72 hours, then at approximately 7 days, then at approximately 2 weeks, and assess signs of severe liver damage:
 - If AST and ALT < 3 fold ULN after 2 weeks, restart at reduced dose. Monitor lab (see above) every week for 4 weeks, then every 2 weeks for at least 8 weeks.
 - If AST and/or ALT \geq 3 fold ULN after 2 weeks or any time thereafter, permanently discontinue study medication.

ALT or AST \geq 8 fold ULN or signs of severe liver damage

- Permanently discontinue study medication.

Proprietary confidential information.

© 2017 Boehringer Ingelheim International GmbH or one or more of its affiliated companies. All rights reserved.

This document may not - in full or in part - be passed on, reproduced, published or otherwise used without prior written permission.

- Patients showing these lab abnormalities need to be followed up according to [Section 10.1.1](#) of this clinical trial protocol and the “DILI checklist” provided in ISF.

Signs of severe liver damage are defined as:

Increase of liver transaminases (ALT or AST \geq 3 fold ULN) and:

- appearance of fatigue, nausea, vomiting, right upper abdominal quadrant pain or tenderness, fever, rash, and/or eosinophilia ($>$ 5%); or

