7.2 NULL AND ALTERNATIVE HYPOTHESES

All analyses in this trial are descriptive and exploratory in nature. No formal statistical inferences are foreseen.

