## 6.7 BASELINE, TIME WINDOWS AND CALCULATED VISITS

As a general rule, last available assessment before first trial drug intake will be used as baseline in 1199.33. If no assessment is available at visit 2, visit 1 will be used as baseline in 1199.33.

A windowing will be performed for all endpoints as described in [Table 6.7: 1](#), in order to assign data to the relevant study visit based on the actual day of the assessment. Data will be analyzed using the re-calculated visits in the statistical tables. However, in the listings, all visits performed will be displayed (even if outside time-window), along with the re-calculated visit. No time-windowing will be performed for the follow-up visit.

Table 6.7: 1 Time windowing rules for spirometry, physical exam, vital signs, pregnancy test

Time window of actual day 			Allocated to		
Start (S n ) day	End (included) (E n ) day	Length of the time-window [days]	Visit number (n)	Visit name	Planned day of the visit (V n )
1	1	1	1 or 2 	Baseline	1
2	22	21	3	2 weeks	15
23	36	14	4	4 weeks	29
37	64	28	5	6 weeks	43
65	127	63	6	12 weeks	85
128	211	84	7	24 weeks	169
212	295	84	8	36 weeks	253
296	393	98	9	48 weeks	337
394	$V_p + (V_{p+1} - V_p)/2 = 505$	$E_p - S_p + 1$	10	64 weeks	449 (V p )
$V_p + 1 + (V_{p+1} - V_p)/2$	$V_{p+1} + (V_{p+2} - V_{p+1})/2$	$E_{p+1} - S_{p+1} + 1$	11	80 weeks	561 (V p+1 )

Table 6.7: 1 Time windowing rules for spirometry, physical exam, vital signs, pregnancy test (cont'd)

...	...	...	...	Every 16 weeks thereafter	V p+2
...	...	...	...	...	V p+...

[1] First trial drug intake date is taken into account as a reference to calculate time windows [2] Depending on the last assessment before first trial drug intake (included), refer to [Section 6.7](#) for baseline definition

Table 6.7: 2 Time windowing rules for laboratory measurements

Time window of actual day 			Allocated to		
Start (S n ) day	End (included) (E n ) day	Length of the time-window [days]	Visit number	Visit name	Planned day of the visit (V n )
1	1	1	1 or 2 	Baseline	1
2	22	21	3	2 weeks	15
23	36	14	4	4 weeks	29
37	64	28	5	6 weeks	43
65	106	42	6	12 weeks	85
107	148	42	6a	18 weeks	127
149	190	42	7	24 weeks	169
191	232	42	7a	30 weeks	211
233	274	42	8	36 weeks	253
275	316	42	8a	42 weeks	295
317	365	49	9	48 weeks	337

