Table 6.7: 2 Time windowing rules for laboratory measurements (cont'd)

366	421	56	9a	56 weeks	393
422	$V_p + (V_{p+1}-V_p)/2$ = 477	$E_p-S_p + 1$	10	64 weeks	449 ( $V_p$ )
$V_p + 1 + (V_{p+1}-V_p)/2$	$V_{p+1} + (V_{p+2}-V_{p+1})/2$	$E_{p+1}-S_{p+1} + 1$	10a	72 weeks	505 ( $V_{p+1}$ )
...	...	...	...	Every 16 weeks thereafter	$V_{p+2}$
...	...	...	...	...	$V_{p+...}$

[1] First trial drug intake date is taken into account as a reference to calculate time windows [2] Depending on the last assessment before first trial drug intake (included), refer to [Section 6.7](#) for baseline definition

For all endpoints, if two post-baseline visits fall in the same time interval after windowing has been applied, the measurement closest to the planned visit will be taken into account. In case two measurements are equidistant from the planned visit, then the last one will be picked.

If after windowing of visits at baseline, two values fall within the same baseline interval, then the last value will be taken into account.

The same rules will be applied for laboratory measurements.

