## 7.8.2 Laboratory data

The analyses of laboratory data will be descriptive in nature and will be based on BI standards (4).

Specific tables will be presented to describe liver enzyme elevations as defined in [Section](#)

5.4.4:

- Summary table of liver enzyme elevation including time to first onset and number of episodes
- Kaplan-Meier plot of time to first liver enzyme elevation (if sufficient number of events). No statistical test will be performed.
- Summary table of individual maximum liver enzyme and bilirubin elevations
- Plot of timecourse profile of liver enzyme for patients having liver enzyme and bilirubin elevation

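### Read literally, the nearest-to-planned-day rule in SAP 6.7 also governs the liver maximum, first-onset, episode and time-course outputs, where retests and end-of-treatment values should count

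*SAP*

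**What the plan says.** SAP 6.7 sets the scope broadly: "A windowing will be performed for all endpoints as described in" Table 6.7: 1. On use, it says: "Data will be analyzed using the re-calculated visits in the statistical tables". On selection, it says: "For all endpoints, if two post-baseline visits fall in the same time interval after windowing has been applied, the measurement closest to the planned visit" is the one used, and a tie goes to the later value. It then adds: "The same rules will be applied for laboratory measurements". One visit is exempt: "No time-windowing will be performed for the follow-up visit". Every visit performed still appears in the listings.

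Neither Table 6.7: 1 nor Table 6.7: 2 has a row for the EOT visit or for unscheduled samples.

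SAP 7.8.2 plans a "Summary table of individual maximum liver enzyme and bilirubin elevations", and also time to first onset, number of episodes, a Kaplan-Meier plot and time-course plots. For the definition of an elevation it points to SAP 5.4.4, and for laboratory methods to a sponsor standard. Neither is in the public text. SAP Table 6.6.1: 1 lists time to first liver enzyme elevation among the endpoints.

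Protocol 4.2.1.2 requires ALT and AST of at least 3 and below 8 fold ULN, without signs of severe liver damage, to be re-tested "within 48 to 72 hours, then at approximately 7 days, then at approximately 2 weeks". Protocol 6.2.2 ties the EOT visit to the last drug intake, not to a planned day. The flow chart has laboratory tests at EOT but none at follow-up.

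**The concern.** Keeping the value nearest the planned day is sound for a by-visit mean. It does not suit a maximum, a first occurrence or a count of episodes, because it selects on timing and ignores the result. Retests are taken because something was abnormal, and EOT values are taken as the patient stops drug. These are the values most likely to compete with a scheduled sample in the same window.

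Long-term safety is the primary objective. Protocol 2.3 names liver enzyme increases among the main risks. ALT or AST of at least 3 fold ULN occurred in 4.9% and 5.2% of nintedanib patients in the two parent trials (Protocol 1.2). Adverse event tables do not fully replace the laboratory tables, because a laboratory change becomes an adverse event only if the investigator judges it clinically relevant (Protocol 5.3.6.1).

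**Working it through.** **1. Reproduce the SAP's windows.** Each window ends midway between planned days: E(n) = (V(n) + V(n+1))/2.
- Table 6.7: 1, week 64: (449 + 561)/2 = 505, as stated.
- Table 6.7: 2, week 64: (449 + 505)/2 = 477, as stated.
- All 8 post-baseline windows with stated limits in Table 6.7: 1 and all 12 in Table 6.7: 2 are reproduced exactly.

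**2. Do the index value and its retests share a window?** Take retests at +3, +7 and +14 days, and the visit tolerances in the flow chart.

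| Laboratory visit | Planned day | Window | Tolerance | Earliest index | Latest 14-day retest |
|---|---|---|---|---|---|
| 5 | 43 | 37-64 | ±3 | 40 | 43+3+14 = 60 |
| 6 | 85 | 65-106 | ±3 | 82 | 85+3+14 = 102 |
| 6a | 127 | 107-148 | ±7 | 120 | 127+7+14 = 148 |
| 7 | 169 | 149-190 | ±7 | 162 | 169+7+14 = 190 |
| 9 | 337 | 317-365 | ±7 | 330 | 337+7+14 = 358 |
| 9a | 393 | 366-421 | ±14 | 379 | 393+14+14 = 421 |
| 10 | 449 | 422-477 | ±14 | 435 | 449+14+14 = 477 |

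From Visit 5 on, all four values fall in one window. In some rows the latest retest lands on the last day, so a retest later than day 14 could slip into the next window. At Visits 3 and 4 with an on-time index, the 3- and 7-day retests share the window and the 14-day retest falls on the next planned day.

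**3. Which of the four is kept?** Let e be the index visit's offset from the planned day and h the tolerance. A retest at +r displaces the index when |e + r| ≤ |e|, that is, when e ≤ -r/2.
- For r = 3 this means e ≤ -2. The 7- and 14-day retests need an earlier visit still.
- The index is therefore kept for e ≥ -1, which is h + 2 of the 2h + 1 whole-day offsets: 5/7 = 71% (±3), 9/15 = 60% (±7), 16/29 = 55% (±14).
- If the first retest is at +2 days, e = -1 is a tie and the later value wins. The shares become 4/7 = 57%, 8/15 = 53% and 15/29 = 52%.

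These shares treat each permitted offset as equally likely. Whichever value is kept, three of the four leave the windowed tables.

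Two invented patients show the two directions under the literal reading:
- 4 fold ULN on day 169 (on time) and 9 fold on day 172: the 4 fold value is kept and the peak is lost.
- At least 3 fold on day 162 (7 days early) and below 3 fold on day 169: the later value is kept and the elevation is lost.

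**4. EOT values.** An EOT before the midpoint falls in the preceding visit's window. With visits on the planned day, the share of days on which EOT loses is:
- days 15 to 29: 7/13 = 54%
- days 85 to 169, Table 6.7: 1: 42/83 = 51%
- each 16-week cycle, Table 6.7: 1: 56/111 = 50%
- each 8-week laboratory cycle, Table 6.7: 2: 28/55 = 51%
- before Visit 3: 0%, as there is no earlier post-baseline value to lose to

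A simulation of 20,000 EOT days, uniform over 1, 3 or 5 years, gives:

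| Setting | Table 6.7: 1 measures | Laboratory |
|---|---|---|
| On-time visits, EOT lost | 50-52% | 50-52% |
| Full visit tolerance, EOT lost | 45-47% | 38-43% |
| Full visit tolerance, EOT replaces the scheduled value | 5-6% | 8-12% |

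The laboratory column applies to ALT, AST and bilirubin, the only tests at the intermediate visits. The follow-up exemption recovers no laboratory value, since none is scheduled at follow-up.

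**The case against.** The strongest reply is that windowing is only a device for allocating data to visits. Its stated purpose is to place each assessment at a study visit. Table 6.6.1: 1 gives time to first liver enzyme elevation its own period without reference to visits, SAP 6.1 takes safety data from first intake to 28 days after last intake, and episodes or time courses make little sense on one value every 6 to 8 weeks. The intention may well be to use all values, and SAP 5.4.4 or the sponsor's laboratory standard may say so. Their absence from the public text is not a fault in the plan.

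That stands as a limit on what can be claimed. It does not remove the conflict. SAP 6.1 and Table 6.6.1: 1 fix the period, not which values within it count, while 6.7 says twice that it covers all endpoints and uses that word as Table 6.6.1: 1 does.

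A reader might also infer stronger things that the documents do not support:
- *That data are discarded.* Unselected values stay in the listings.
- *That all three retests are always lost.* That holds when the index is on or after the planned day. An earlier index may itself be displaced.
- *That time to first elevation is always distorted.* A retest follows a value already at or above 3 fold ULN. If that value is kept, first onset and the 3 fold incidence do not change because of dropped retests.
- *That half of EOT values are lost as a fact.* The share rests on uniform stopping times and falls if patients stop at scheduled visits.
- *That vital signs and weight look safer.* No direction is shown for vital signs, and no weight table is visible; weight decrease is tabulated as an adverse event.
- *That the primary endpoint is affected.* Adverse event incidence, the hepatic adverse event groupings in SAP 7.8.1 and time to death do not use these windows.

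**Conclusion.** The point holds as a defect in the wording of SAP 6.7 that should be corrected. Applied as written, the rule would give wrong individual maxima and episode counts, and sometimes a wrong first onset, because one of four values is kept per window of 42 days or more and the choice depends on visit timing. EOT values early in an interval can lose in the same way: about 38% to 52% of them, assuming uniform stopping between visits.

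Whether the reported liver tables would actually change cannot be settled from the public text. If SAP 5.4.4 or the laboratory standard already uses all values, 6.7 contradicts them and a clarifying sentence is enough. If not, the liver results depend on the correction. The protocol states that "No formal statistical inferences are foreseen", so no test or error rate is involved; the issue is the accuracy of descriptive safety tables.

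**What to change.** Make two changes to the SAP text:

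1. In 6.7, restrict the nearest-to-planned-day rule to by-visit summaries.
2. In 6.7 or 7.8.2, state that the individual maximum, first-onset, episode and time-course liver outputs use every value in the on-treatment period defined in 6.1, scheduled or unscheduled, including EOT.

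A separate row for the last on-treatment value in the by-visit tables would be a presentational choice and is not needed to resolve the point.

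The cost is about two sentences and some programming. Unselected values are already listed, so no new data are needed. The downside is that the liver elevation figures may become slightly less favourable.

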## **7. PLANNED ANALYSIS**

For End-Of-Text (EoT) tables, the set of summary statistics is: N / Mean / SD / Min / Median / Max.

Tabulations of frequencies for categorical data will include all possible categories and will display the number of observations in a category as well as the percentage (%) relative to the respective treatment group (unless otherwise specified, all patients in the respective patient set whether they have non-missing values or not). Percentages will be rounded to one decimal place. The category missing will be displayed only if there are actually missing values.

### **7.1 DEMOGRAPHIC AND OTHER BASELINE CHARACTERISTICS**

Only descriptive statistics are planned for this section of the report.

### **7.2 CONCOMITANT DISEASES AND MEDICATION**

According to the CTP, there are fewer restrictions in concomitant therapies in 1199.33 as compared to parent trial. No comparison is therefore possible between parent and extension trial, even for placebo-randomized patients in parent trial.

Baseline therapies will be defined as treatments with a start date before first trial drug intake in extension trial and taken after or on the day of the first trial drug intake in extension trial.

On-treatment concomitant therapies are defined as treatments with a start date after or on the day of first trial drug intake in extension trial and before or on the day of last trial drug intake in extension trial.

A summary of all on-treatment concomitant therapies (including baseline CTs) will be provided by randomised treatment in parent trial, ATC3 codes and Preferred Name (PN) (sorted by alphabetical ATC class and decreasing frequency of preferred names within ATC class).

Post-study drug discontinuation therapies are defined as treatments started between last trial drug intake and the latest between trial completion and last drug intake + 28 days (included). They will be summarized by randomised treatment in parent trial, ATC3 codes and Preferred Name (PN). This aims at flagging concomitant treatments taken by patients after they have stopped the study drug.

Relevant groups of therapies have been defined as Special Search Categories (SSC) or Standardised Drug Groupings (SDG). These are listed in [Section 9.3](#).

The summary of all on-treatment concomitant therapies (baseline CTs and on-treatment CTs) will also be performed by Special Search Category (SSC) or Standardised Drug Groupings (SDG) and Preferred Name (PN) (sorted by alphabetical SSC or SDG and decreasing frequency of preferred names within SSC).

Only descriptive statistics are planned for this section of the report.

### **7.3 TREATMENT COMPLIANCE**

Only descriptive statistics are planned for this section of the report.

### **7.4 PRIMARY ENDPOINT(S)**

There is no primary endpoint as the primary objective of the trial is to assess the safety of Nintedanib, so please refer to [Section 7.8](#).

[figure not shown]
### **7.5 SECONDARY ENDPOINT(S)**

[figure not shown]
#### **7.5.1 Key secondary endpoint(s)**

This section is not applicable as no key secondary endpoint has been specified in the protocol.

#### **7.5.2 (Other) Secondary endpoint(s)**

This section is not applicable as no secondary endpoint has been specified in the protocol.

## **7.7 EXTENT OF EXPOSURE**

The data will be analysed on the Treated Set.

A summary table showing the duration on treatment (both mean and frequency in classes, see [Section 5.4.3](#)) will be performed.

A table displaying the disposition of patients and the conclusion of patients' participation, and a table displaying the primary reason for non-inclusion will be provided.

The proportion of patients on each dose actually taken at visit 2 will be displayed according to:

- randomized treatment group in parent trial (by parent trial and both combined)
- the dose actually taken at the end of parent trial (by parent trial and both combined)
- the dose actually taken at the end of 1199.33 extension trial

A summary of treatment interruption will be performed including number of patients with at least one interruption, number and reason of interruptions, as well as time to first treatment interruption in 1199.33. A similar summary will be performed for dose change.

Besides, a summary table showing the duration on actual treatment dose (both mean and frequency in classes, see [Section 5.4.3](#)) and off-treatment duration will be performed by randomized group of the parent trial. This will take into account the actual dose following dose reductions or increases.

Kaplan-Meier plots of time to permanent treatment discontinuation will be drawn by randomised treatment in parent trial and overall. Similarly, Kaplan-Meier plots will be performed for time to first dose reduction and for time to first treatment interruption by randomised treatment in parent trial and overall. No statistical tests will be performed.

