In the IPF phase II proof-of-concept trial 1199.30, 432 patients with consistent IPF were randomized, with baseline characteristics comparable across groups. The results of the primary endpoint analyses, annual rate of FVC decline, were: 0.19 L (placebo); 0.17 L (50 mg qd); 0.21 L (50 mg bid); 0.16 L (100 mg bid); and 0.06 L (150 mg bid: -68% reduction in rate of decline vs. placebo, $p=0.0136$; closed-testing multiplicity corrected: $p=0.0639$). At end of study, FVC% pred was better preserved in the 100 mg bid ($p=0.0314$) and 150 mg bid ($p=0.0002$) groups when compared to placebo. FVC signal robustness was supported by results of body plethysmography and oxygen saturation. Compared to placebo, fewer patients had acute exacerbations in the 150 mg bid group ($p=0.0150$), and there were a greater number of SGRQ 4-point scale responders in the 100 mg bid ($p=0.0069$) and 150 mg bid ($p=0.0341$) groups. No effect was observed on DL_{CO} and 6-MWT. The number of deaths was not

Proprietary confidential information.

© 2017 Boehringer Ingelheim International GmbH or one or more of its affiliated companies. All rights reserved.

This document may not - in full or in part - be passed on, reproduced, published or otherwise used without prior written permission.

significantly different between groups. Discontinuations (26.2%; 22.4% due to AE) were more frequent with 150 mg bid (37.6%; 31.8%), but less with 100 mg bid (16.3%; 15.1%), compared to placebo (28.2%; 24.7%).

The adverse events most frequently leading to discontinuation were diarrhoea, nausea, and vomiting (in the group receiving 150 mg twice a day as compared with those receiving placebo, the respective rates were 11.8% vs. 0%, 4.7% vs. 0%, and 2.4% vs. 1.2%). Among the 85 patients in the group receiving 150 mg of the study drug twice a day, 4 (4.7%) had serious gastrointestinal events and 5 (5.9%) had severe gastrointestinal events, especially diarrhoea, as compared with no patients in the placebo group.

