### 6.6.1 Time to event endpoints

Missing data for time-to-event endpoints are managed by censored data analyses. No specific procedures need to be specified to handle them.

If a patient has no event during the studied period then he will be censored on the day corresponding to the end date of the studied period. The studied period for each type of endpoint is detailed in [Table 6.6.1: 1](#).

Table 6.6.1: 1                      Censoring rules for time to event endpoints

Endpoint	Studied period	Censoring rule
Time to death Time to first IPF acute exacerbation	From first trial drug intake in 1199.33 to last contact date	Patients with no event at the cut-off date will be censored at their last contact date
Time to first dose reduction Time to first treatment interruption Time to permanent treatment discontinuation	From first trial drug intake in 1199.33 to last trial drug intake	Patients with no event at the cut-off date will be censored at their last trial drug intake
Time to first occurrence of adverse event of particular note Time to first liver enzyme elevation	From first trial drug intake in 1199.33 to last trial drug intake + 28 days	Patients with no event at the cut-off date will be censored at their last trial drug intake + 28 days

Cut-off date = Date of the interim database lock

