The frequency of patients with adverse events will be summarised by randomised treatment in parent trial, primary system organ class and preferred term. Separate tables will be provided for patients with other significant adverse events according to ICH E3 (3), for

patients with serious adverse events, for patients with adverse events occurring with an incidence in preferred term greater than 5% (in at least one treatment arm), for patients with protocol specified significant adverse events (as ticked in the AE page of the CRF), for patients with related adverse events, for patients with adverse events leading to dose reduction and for patients with adverse events leading to treatment discontinuation.

The system organ classes will be sorted according to the standard sort order specified by EMA, preferred terms will be sorted by descending frequency over the total column (within system organ class).

Specific tables will be created in order to describe selected adverse events of particular note, such as diarrhoea events:

- Display of the diarrhoea specific page of the CRF
- Summary of diarrhoea events including time to onset, number and duration of episodes
- Summary of diarrhoea adverse events including seriousness, clinical consequences (dose -reduction, drug discontinuation or drug interruption) and outcome
- Kaplan-Meier plots of time to first diarrhoea event, by randomised treatment in parent trial and overall

Specific summary tables including seriousness, clinical consequences and outcome will also be presented to describe the following adverse events of particular note: nausea, vomiting, dehydration and weight decrease adverse events. Depending on the number of patients having such adverse events, summary tables including time to onset, number of episodes and duration together with Kaplan-Meier plots of time to first event, by randomised treatment in parent trial and overall, may also be produced with and without a y-axis cut-off at 70%.

Topics or syndromes that are medically relevant to the clinical development program are specified in [Table 7.8.1: 1](#). The frequency of patients with AEs within these topics or syndromes will be summarised by treatment, topic or syndrome and preferred term. A separate table will be provided for patients with serious AEs (SAEs), by treatment, topic or syndrome and preferred term.

Table 7.8.1:1 Aggregated adverse events by topic or syndrome

Organ system	Topic or Syndrome	Term selection

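### Death and clinical permanent discontinuation are plain censoring in the on-treatment Kaplan-Meier curves, so 1-KM at later times exceeds the proportion of patients affected

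*SAP*

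**What the plan says.** SAP 7.7 plans Kaplan-Meier plots of time to permanent discontinuation and then adds: "Similarly, Kaplan-Meier plots will be performed for time to first dose reduction and for time to first treatment interruption". SAP 7.8.1 plans "Kaplan-Meier plots of time to first diarrhoea event, by randomised treatment in parent trial and overall". For nausea, vomiting, dehydration and weight decrease such plots are optional. SAP 7.8.2 plans one for first liver enzyme elevation, provided there are enough events.

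The censoring rules are in SAP 6.6.1, Table 6.6.1:1. For first dose reduction and first interruption: "Patients with no event at the cut-off date will be censored at their last trial drug intake". For adverse events of particular note and liver elevation the studied period is "From first trial drug intake in 1199.33 to last trial drug intake + 28 days", with censoring at its end. The table does not distinguish a patient who died, one who stopped for toxicity or progression, and one still on drug at the cut-off. The lead-in text says: "Missing data for time-to-event endpoints are managed by censored data analyses. No specific procedures need to be specified to handle them".

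No visible part of the SAP names a cumulative incidence method or a competing event. SAP 7.7 does plan crude figures, "including number of patients with at least one interruption, number and reason of interruptions", and a similar summary for dose change. SAP 7.8.1 bases all adverse event analyses on numbers of patients.

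**The concern.** A patient who has died or stopped the drug for good can no longer have a dose reduction or an interruption, nor an on-treatment adverse event beyond 28 days after last intake. Censoring that patient gives him the same future risk as those who remain on drug. The curve then estimates the event probability as if nobody died or stopped, which differs from the proportion who have the event on treatment.

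The setting leaves room for the difference to grow. The protocol expects the trial to last about 6½ years (3.1) and gives an average life expectancy of 2 to 3 years in this disease (1.1). Long-term safety is the sole objective (2.2), so the late part of each curve will attract attention. The same report would carry crude patient counts that may be well below the late curve values, with nothing to explain why.

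**Working it through.** The documents give no figure for any of these curves, so there is nothing to reproduce. The check compares the two estimands under stated assumptions.

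**Direction.** When competing exits are treated as censoring, 1-KM is at or above the Aalen-Johansen cumulative incidence at every time. It is strictly above once a death or permanent stop precedes a later event. This needs no assumption about rates.

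**Formulas.** With constant event hazard L and constant hazard C of death or permanent stop:
- 1-KM(t) = 1 − exp(−Lt)
- CIF(t) = L/(L+C) × [1 − exp(−(L+C)t)]

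**Inputs.**
- Stop rates: phase II discontinuation in Protocol 1.2, namely 16.3% (100 mg bid), 26.2% (overall) and 37.6% (150 mg bid), read as one-year rates and taken to cover death on drug. C = −ln(1−d) gives 0.178, 0.304 and 0.472 per year.
- Event hazards: 0.15 and 0.05 per year. Both are assumptions.

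**One case in full** (L = 0.15, C = 0.304):
- Year 1: 1-KM = 1 − exp(−0.15) = 13.9%; CIF = 0.15/0.454 × [1 − exp(−0.454)] = 12.1%. Gap about 2 points.
- Year 2: 25.9% against 19.7%. Gap about 6 points.
- Year 4: 1 − exp(−0.60) = 45.1% against 0.330 × [1 − exp(−1.816)] = 27.7%. Gap about 17 points.

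**Range at 4 years.**

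| Event hazard per year | 1-KM | CIF, stop 16.3% | CIF, stop 26.2% | CIF, stop 37.6% | Gap (points) |
|---|---|---|---|---|---|
| 0.15 | 45.1% | 33.4% | 27.7% | 22.1% | 11.7 to 23.0 |
| 0.05 | 18.1% | 13.1% | 10.7% | 8.4% | 5.0 to 9.7 |
| 0.25 in year 1, then 0.05 | 33.0% | 27.4% | 24.5% | 21.5% | 5.5 to 11.5 |

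For the 0.05 hazard and the 26.2% stop rate, the year 1 gap is about 0.7 points.

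**Anchored to a documented rate.** Protocol 1.2 gives transaminase elevation of at least 3 times ULN in 4.9% and 5.2% of nintedanib patients in the parent trials. With L solved so that the 1-year CIF is 5%, the 4-year values run from 20.1% against 14.6% (stop 16.3%) to 22.8% against 10.6% (stop 37.6%). The year 1 excess is 0.5 to 1.3 points.

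**Early events.** If 65% of patients are susceptible to diarrhoea with a mean onset of 2 months (both assumed), the 4-year figures are 65% against 63% at a 16.3% stop rate and 65% against 60% at 37.6%.

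**Simulation.** In 60 simulated trials of 750 patients (L = 0.20, C = 0.331, administrative censoring at 4 to 5.2 years), the averages were 54.6% for 1-KM at 4 years, 33.0% for Aalen-Johansen at 4 years, and 34.1% for the crude proportion.

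**The case against.** **The proportion affected is reported elsewhere.** The primary endpoint is the number and percentage of patients with adverse events, and SAP 7.7 counts patients with interruptions and dose changes. In the simulation the crude proportion lies close to Aalen-Johansen. No test or decision rests on the plots (Protocol 7.2). This stands, and it limits the harm to how the curves are read. A reader might infer that the report will misstate how many patients had these events; the planned counts do not support that.

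**Kaplan-Meier on treatment answers a fair question.** Under independent censoring it estimates risk while the drug is continued. This also stands, so the case is for an added curve and a label. The SAP does not say that this is the target.

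**The stop rates may not transfer.** They are phase II rates carried forward as constant. Patients here completed 52 weeks, and those who did not tolerate or who discontinued the blinded drug are ineligible (Protocol 2.3, 3.3.2). The sizes are therefore illustrative.

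**Informative censoring is easily overstated.** In phase II, 31.8 of the 37.6 points of stopping on 150 mg bid were attributed to adverse events, and a reader might take all of that as intolerance that biases every curve. The documents do not support this. The current protocol records worsening of the underlying disease as an adverse event (5.3.6.1). A patient who stops because of diarrhoea already counts as an event on the diarrhoea curve. The mandatory stop for recurrent diarrhoea applies after a dose reduction (3.3.4.1), so that patient normally has an event on the dose-reduction curve too. Applying the all-cause stop rate to each curve ignores this overlap.

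**Administrative exits.** A reader might also infer that most patients will leave by death or a clinical stop. That is undocumented: the rationale for Amendment 3 says the trial is being ended in the countries where the drug is now accessible, which are most of those taking part. Ordinary censoring suits those exits.

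**Scope.** The liver plot and several adverse event plots are conditional. Some SAP sections, including the endpoint definitions cited in 7.7 and 7.8.2, are not visible, so the absence of a competing-event method is judged on the visible text.

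**Conclusion.** The point holds as a matter of interpretation and labelling. As specified, the curves treat death and clinical permanent discontinuation as ordinary censoring, and 1-KM read as the proportion affected on treatment is too high at later times. The direction is certain wherever such exits precede later events.

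The size is not certain. It is about 2 points or less at year 1 in the cases at the 26.2% stop rate with event hazards of 0.05 or 0.15 per year, small throughout for early events such as diarrhoea, and roughly 5 to 23 points at 4 years for events that accrue over years. Those figures rest on assumed event hazards, constant stop hazards, and phase II stop rates that may be too high for a population that has already completed a year. The documents do not support a finding that the Kaplan-Meier plots are invalid or must be withdrawn.

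**What to change.** In SAP 6.6.1, 7.7, 7.8.1 and 7.8.2:
- Add Aalen-Johansen cumulative incidence curves for first dose reduction, first interruption, first diarrhoea, any other adverse event of particular note that is plotted, and first liver enzyme elevation if plotted.
- Define death and clinical permanent discontinuation as competing events. Keep data cut-off, closure by the sponsor and a switch to drug available outside the trial as censoring. The reason for discontinuation is already recorded in the eCRF (Protocol 3.3.4.1, 6.2.2).
- Keep the Kaplan-Meier plots, with a label saying that they show risk while treatment continues.

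The cost is SAP wording and a little more programming; no new data are needed. The downside is that the cumulative incidence curves depend on this trial's stop rate and are not directly comparable with earlier Kaplan-Meier plots, which is a further reason to keep both.
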